2) Once the HTKs become available for use and pass the TPP requirements, individuals will be invited to participate in stage two based on a combination of stratified and random sampling, if necessary, based on geography, age, symptom history and EIA result. During this stage, an additional blood sample will be taken. Individuals who complete the HTK will do so independently, and will also take a photograph of their HTK result. Comparative accuracy of reading of HTK results by trained professionals (in the community, and by photograph) will also be explored. Data from this stage will

Evaluating Detection of SARS-CoV-2 antibodies using home test kits (EDSAB-HOME study)

Protocol 30.05.2020 Version 04.03

allow us to assess agreement between user reading, reading of test results by a trained professional in the community and using a photograph, and reading in a laboratory setting. This will allow us to determine whether accuracy estimates from stage one are applicable to these other types of reading. (Objective 2, 3, 5, 6).

All participants will be followed up with weekly symptom questionnaires and linked to routine laboratory and hospital record statistics, to identify progression to severe COVID-19 disease (and possibly mild COVID-19 disease, confirmed microbiologically, depending on changes to future testing strategy) (Objective 4).

In the event that antibody kits are available earlier than expected, and at scale, stage one and two may be combined with all subjects in stage one (above) additionally doing POC tests. In addition, depending on operational capacity, stage two and stage three may also run in parallel.

3) The service evaluation will be extended when the programme expands to home use; however, the evaluation will focus on assessing the usability and accessibility of the programme and to identify any logistical/operational limitations associated with the home delivery system, and where improvements may be required. In addition, the three-stage service evaluation may be extended at a later date to the general population, contingent on sufficient clinical performance of the HTK within the healthcare workers and police officers. (Objective 5)

Figure 1: Overview of the three-stage evaluation study methodology

Recruitment sites and study areas will reside within the UK, and will be chosen based on the epidemiology and operational capacity available during the study launch.

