- 12. The lithium heparin anticoagulated sample is sent to Oxford Immunotec Ltd, Milton Park, Oxford for T-SPOT SARS-CoV-2 testing. This is a Research Use only (RUO) ELISPOT based kit produced by Oxford Immunotec which is due to be launched on 15 May 2020. It measures the number of CD4 and CD8 cells specifically producing interferon-γ in response to a proprietary mixture of proteins and/or peptides derived from SARS-CoV-2 proteins. The tube sent to Oxford Immunotec will be identified by a study number only. Oxford Immunotec return the results to PHE.
- 13. Banked plasma is analysed for anti-SARS-CoV-2 antibodies using the HPA EIA assay, and other assays as they are developed. Additional samples (capillary blood and/or dried blood spot) will also be banked and despatched to laboratories as directed by the DHSC program evaluating team.
- 14. Banked plasma is made available for laboratory evaluation of HTKs in a laboratory setting, when such kits become available.
- 15. If the subject has requested the result of their serological results, we will provide them when
 - The assays used have been deployed, or are scheduled for deployment, by the NHS at the time of reporting, and so are considered to have a sufficient level of validation.
 - We have sufficient confidence in the technical processes.

Substantial uncertainty remains about the clinical interpretation of these tests (for example – are the individuals protected if seropositive), and data is accruing all the time. The NHS is currently drawing up interpretation guidelines. We will provide the results with an explanation congruent with those issued by the NHS when these complete. We will test these materials with the HRA's Patient and

Evaluating Detection of SARS-CoV-2 antibodies using home test kits (EDSAB-HOME study)

Protocol 30.05.2020 Version 04.03

Public Involvement group before we use them, and provide a report on this activity to the PHE REC before going ahead.

In all cases we will state that, in the event that clinical decisions need to be made based on antibody levels, the subjects should have a test performed by an NHS Laboratory at the relevant time. This is because antibody levels may change over time.

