16. The subject is followed up by PHE actively, with weekly symptom and activity questionnaires, and passively, with weekly database (SGSS, a microbiology database containing COVID-19 results, and other appropriate queries) searches for all evaluated subjects, allowing quantification of hospitalisation with positive SARS-CoV-2 tests, a proxy for severe disease.

Study workflow (Stage two, Community testing centre):

- 1. The subject is asked to give consent to testing a HTK.
- 2. The subject is asked to complete short questions on their current behaviour over the prior weeks.
- 3. Up to 20ml venous blood sample will be obtained by a trained on-site phlebotomist exactly as in Stage 1.
- 4. The subject does a HTK without assistance, using the packaging and training proposed for home use.
- 5. The subject may optionally be asked to read the result not of their own test, but of another person, following a randomisation procedure to which the subject is blinded. The necessity for this step is discussed in Objective 2, below.
- 6. The subject takes a photo of the result on their mobile phone (perhaps with the NHSX or another appropriate app), and/or uploads the result to the NHSX designed app, or via another appropriate tested mechanism agreed with MHRA.
- 7. The result will also be independently read by a trained professional and a second independent reviewer and/or algorithm (e.g. in-app test reader).
- 8. The subject completes an additional questionnaire, including questions on ease of use and reading of the kits, acceptability of the kits etc. In some cases, structured, semi-structured interviews may occur.
- 9. The subject is thanked, given a leaflet or email providing contact details if they have any further questions.
- 10. The blood sample is sent to PHE Sero Epidemiology Unit (SEU) Laboratory in Manchester, and/or another laboratory as necessary, and analysed for anti-SARS-CoV-2 antibodies using the HPA EIA assay, and other assays as they are developed. Other experimental assays may also be used.
- 11. The lithium heparin anticoagulated sample is sent to Oxford Immunotec Ltd and processed exactly as in Phase 1.
- 12. The HTK is repeated in the laboratory on the blood sample taken, to determine whether results are the same as from the HTK when done in the community testing centre.
- 13. The subject continues to be followed up by PHE actively, and passively, as outlined previously.

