To describe the numbers of coronavirus responsive T cells in peripheral blood of subjects using ELISPOT technology, and its relationship to serological tests for SARS-CoV-2, and to clinical risk factors for COVID-19;

Evaluating Detection of SARS-CoV-2 antibodies using home test kits (EDSAB-HOME study)

Protocol 30.05.2020 Version 04.03

We will analyse the number of coronavirus responsive T cells, as determined by T-SPOT Coronavirus, as a continuous variable, describing its relationship with age, gender, ethnic group, occupation, recent symptoms and previous exposure to SARS-CoV-2 assessed using symptoms and previous positive tests, as well as with enzyme immunoassay results. Some of these data may be useful as part of a regulatory package applying for regulatory approval of T-SPOT coronavirus tests for clinical use. Discussions as to the appropriate analysis of this data are ongoing between Oxford Immunotec Ltd and MHRA. An appendix pre-specifying these analyses will be added to this protocol when these discussions are complete.

Objective 7

To provide estimates of the hazard of development of COVID-19 compatible symptoms, or of COVID-19 related hospitalisation, among individuals with a positive vs negative laboratory and HTK antibody test kit results, and its relationship to SARS-CoV-2 responsive T cells from the T-SPOT Coronavirus test;

Development of COVID-19 compatible symptoms will be assessed through the weekly follow-up text or email messages. Development to COVID-19 related hospitalisation will be assessed through data linkage to routine laboratory and hospital record systems (SGSS and HES). These will be exploratory end-points, with the acknowledgment that we may be underpowered to detect the rarer, severe endpoints (e.g. hospitalisation) within our current cohort. However, this step aims to assess the feasibility of the process, and may lead to a secondary follow up study (e.g. linkage of the first 50,000 who use this service to laboratory and hospital records) to estimate the rate of development to COVID-19 related hospitalisations, if operationally feasible.

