Descriptive statistics, frequency and percentages (life tables) will be used to describe outcomes, split by exposure type. Exposure of primary interest will be considered HTK result (positive or negative), laboratory based EIA result, and SARS-CoV-2 responsive T cell numbers, determined by T-SPOT Coronavirus assays, and outcome will be considered either COVID-19 compatible symptoms and/or progression to severe COVID-19 disease, as defined operationally by hospitalisation.

Secondary exposures of interest will include age, sex, exposure to known confirmed case, occupation, behaviour (i.e. at work or self-isolation), co-morbidities, and other risk factors. We will model the hazard of a COVID-19 related outcome (symptoms, hospitalisation) over time accounting for subject factors as covariates, using generalised linear mixed models and cure-rate type time-to-event models accounting for time-varying covariates.

Objective 8

To provide a panel of plasma which can be used for proficiency testing and batch release assay.

Plasma will be stored in PHE for this purpose. We will work to bank these materials in an NIHR Biorepository.

Other considerations

Safety Considerations

There is little risk to the subjects. A trained phlebotomist or research nurse will collect up to 20ml of blood from individuals, which is a small volume (about 5% of the amount donated at blood donation). Some

Evaluating Detection of SARS-CoV-2 antibodies using home test kits (EDSAB-HOME study)

Protocol 30.05.2020 Version 04.03

people may feel faint when they give blood, but this is transient and is not harmful. Some bruising may occur where the blood is taken, but this is also transient and harmless. All benefits are indirect, and will inform the programme's implementation and subsequent public health advice.

Benefits of taking part

Participants will receive the results from the laboratory-based tests, if they wish to do so. If they take part in stage two, they will have access to HTK results indicating whether they have antibodies against COVID-19. The volunteers contribute to the development and evaluation of the SARS-CoV-2 antibody testing programme.

Dissemination of Results and Publication Policy

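### Objective 7 compares antibody groups on unconfirmed, self-reported symptoms, so its hazard ratio is diluted and open to reporting bias, while confirmed infection outside hospital is not a named outcome

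*Protocol*

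**What the plan says.** Protocol, Objective 7, sets two outcomes for the comparison by HTK result, laboratory result and T-SPOT count: the "outcome will be considered either COVID-19 compatible symptoms and/or progression to severe COVID-19 disease, as defined operationally by hospitalisation". On the first it says: "Development of COVID-19 compatible symptoms will be assessed through the weekly follow-up text or email messages". No confirmation step follows. Hospitalisation is found by linkage to SGSS and HES. The same section calls the endpoints exploratory and warns of low power for the rarer, severe ones.

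Stage one workflow, step 16, describes passive follow-up "with weekly database (SGSS, a microbiology database containing COVID-19 results, and other appropriate queries) searches for all evaluated subjects", and gives its use as "allowing quantification of hospitalisation with positive SARS-CoV-2 tests, a proxy for severe disease". The stage-two text under Three stages says that linkage is to identify severe disease "and possibly mild COVID-19 disease, confirmed microbiologically, depending on changes to future testing strategy". It tags this to Objective 4, which is acceptability.

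On disclosure, Benefits of taking part states: "Participants will receive the results from the laboratory-based tests, if they wish to do so". Step 15 of the stage one workflow adds conditions, one being: "The assays used have been deployed, or are scheduled for deployment, by the NHS at the time of reporting". Stage-two participants have access to their HTK result, and stage-three users record their own. Objective 2 notes that results from outside the study are increasingly available, and treats knowledge of the expected result as a source of bias in reading the kit.

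**The concern.** Antibody to SARS-CoV-2 cannot lower the rate of compatible symptoms that have another cause. Such episodes enter both groups and pull the symptom hazard ratio towards 1. The symptom outcome is also self-reported, and some participants will know the exposure being compared, so reporting may differ by that exposure.

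Because hospitalisation may be too rare to be informative, symptoms are likely to supply most of the usable events. A weak hazard ratio could then mean weak protection or a non-specific endpoint. A low one could mean protection or under-reporting by people who believe themselves immune. Without confirmed events, a reader cannot tell these apart. Whether antibody translates into protection in the field is one of the unknowns that the protocol lists as driving its staged design.

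**Working it through.** Objective 7 states no sample size, event count, hazard ratio or power, so there is no figure to reproduce.

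**1. Passages side by side.**
- Step 16 of the stage one workflow: SGSS results are searched weekly, and the stated use is hospitalisation with a positive test.
- Stage-two text: confirmed mild disease may possibly be captured, under Objective 4.
- Objective 7: symptoms and hospitalisation only.

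Confirmed infection outside hospital is thus raised in one place and missing from the objective it would serve.

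**2. Dilution.** Let p be the share of symptom episodes in seronegatives caused by SARS-CoV-2. Assume equal rates of other compatible illness in both groups. Then

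HR observed = (1 − p) + p × HR true.

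With an assumed 90% protection (HR true 0.10) this is 1 − 0.9p:

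| p | HR observed |
|---|---|
| 50% | 1 − 0.45 = 0.55 |
| 20% | 1 − 0.18 = 0.82 |
| 10% | 1 − 0.09 = 0.91 |
| 5% | 1 − 0.045 = 0.955 |

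The result depends far more on p than on the assumed protection. For HR true from 0.05 to 0.20, the observed value runs from 0.525 to 0.60 at p = 50% and from 0.905 to 0.92 at p = 10%.

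The documents do not give p. As illustration with assumed weekly rates, 0.1% for COVID-19 and 1% for other compatible illness give p = 0.1/1.1 = 9% and HR 0.92. Rates of 0.5% for each give p = 50% and HR 0.55.

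**3. Effect on power.** Schoenfeld's formula is D = (1.96 + 0.84)² / [π(1 − π)(ln HR)²], for two-sided 5% and 80% power, both assumed. For the seropositive share π, 10% is the seroprevalence that the protocol assumes for its capillary subsample; 20% is a sensitivity value.

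| HR observed | Events needed, π = 10% | Events needed, π = 20% | Power with an assumed 500 events, π = 10% |
|---|---|---|---|
| 0.55 | 245 | 138 | 98% |
| 0.91 | 9,805 | 5,516 | 9% |

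**4. Differential reporting.** If seropositives report at r times the rate of seronegatives, the observed ratio is multiplied by r. With assumed values of r:
- Starting from 0.91: r = 0.7 gives 0.64, and r = 1.2 gives 1.09.
- Starting from 0.55: r = 0.7 gives 0.385, and r = 1.2 gives 0.66.

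The distortion can run either way.

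**5. A confirmed outcome.** With no unrelated illness in the endpoint the ratio stays at 0.10, and the formula gives about 17 events (π = 10%) or 10 (π = 20%). These are orders of magnitude only. Of 17 events, about 17 × 0.01/0.91 = 0.2 would be expected in seropositives, too few for the approximation to be trusted.

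**The case against.** Several stronger readings are tempting, and the protocol does not support them.

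- *That the symptom hazard ratio will sit near 1 even under strong protection.* This needs about 90% or more of episodes to be unrelated to SARS-CoV-2. At 50% the ratio is 0.55 and readily detectable.
- *That swab results are not used as an endpoint.* Hospitalisation is ascertained through SGSS and HES and uses positive tests. Only confirmed infection outside hospital is missing.
- *That all participants are told their result.* Release is opt-in and conditional. T-SPOT, a third primary exposure, is a research-use kit whose results return to PHE; as written, the release step would not cover it. Dilution still applies to that comparison.
- *That behaviour change is ignored.* Weekly activity questionnaires, covariates for behaviour and known-case exposure, and models with time-varying covariates are planned. They address changed exposure, not changed reporting.
- *That SGSS positivity should be the main outcome.* Analysis 1b says that testing after early March was largely confined to hospitalised cases, which is a fair reason for keeping confirmed mild disease conditional. People who know they are seropositive may also seek swabs less.

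Objective 7 is also exploratory, is partly a feasibility exercise, and carries no decision rule. An unseen SAP could hold the modelling detail. What remains is that the outcome definition stands in the protocol itself, and its caveat covers only the rarity of severe events. A larger sample cures neither dilution nor reporting bias. The date on which a participant learned a result must be collected during follow-up, because it may not be recoverable later.

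**Conclusion.** The point holds in limited form. As written, Objective 7 yields a symptom hazard ratio that is diluted by other illness and, among those who know their result, open to reporting bias in either direction. The protocol acknowledges neither for this objective.

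The dilution is modest or severe depending on a share that the documents do not give: from 0.55 to 0.91 as that share falls from 50% to 10%, assuming 90% protection and equal background illness in both groups. A reader might infer that Objective 7 cannot be answered at all. That goes too far, since the record-linked hospitalisation outcome remains and the symptom ratio is still informative if the share is high. The supported conclusion is that the symptom outcome alone cannot be reliably interpreted as evidence on protection. This is a cheap improvement to an exploratory objective, not a flaw in the accuracy evaluation.

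**What to change.** 1. Reconcile the stage-two follow-up text, step 16 of the stage one workflow and Objective 7. Name the first new SARS-CoV-2 positive result in SGSS after the baseline sample as an additional exploratory outcome of Objective 7, alongside symptoms and not replacing them. Correct the Objective 4 tag.
2. State in Objective 7 that the symptom outcome is non-specific, that unrelated illness biases its hazard ratio towards 1, and that knowledge of the result may distort it either way.
3. Record the date each participant learned an antibody result: the study release date, plus one weekly questionnaire item for outside tests. Use it as a time-varying covariate or in a sensitivity analysis limited to follow-up before disclosure.

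The cost is protocol wording, one questionnaire item and use of a database already searched. The protocol should also state the downsides: confirmed events will be few, they depend on access to testing, and swab uptake may itself differ by known antibody status. The new outcome therefore reduces the problem of non-specific events but does not remove bias from disclosure.

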APPENDIX ONE

Serological responses to SARS-CoV-2:

Specificity: The specificity of a test refers to the proportion of individuals without the condition who test negative.

Humans make antibodies against coronaviruses following infection, predominantly against the Spike (S) and nucleoproteins (N) (1). Four coronaviruses circulate in the general population, and a high proportion of the population has antibodies against these HKU1, 229E, NL63 and OC43 coronaviruses (2). This is a potential challenge for antibody based tests given homology between coronaviruses; for the application proposed, a highly specific assay (i.e. one which is positive only if individuals are recently exposed to SARS-CoV-2, without false positive tests). Nevertheless, there are indications such specific detection is possible:

- Immune responses against the S1 component of the Spike protein, or the receptor-binding domain (RBD) within it, appear specific to SARS-CoV2, although responses against S2 as more cross reactive predominantly against the Spike (S) and nucleoproteins (N) (1).
- Following SARS-CoV-2 infection, IgG, IgM and IgA responses are generated against the spike protein (3); sensitivity of assays detecting IgA may be slightly higher than that of assays using IgG (2).
- Serological assays against S protein (EIA signal) are strongly correlated with neutralisation assays (2) (4).
- Commercial assays for components of SARS-CoV-2 S protein and N protein are becoming available. One example is a CE marked Enzyme Immunoassay (EIA) from Euroimmun. There are reports of a potential cross reactivity in 2/60 samples from one plasma set analysed using this kit (2), and validation work done in PHE Porton Down¹ found one strong positive and one indeterminate result in 92 samples believed to be negative (Tables 1,2 reproduce data from report cited in footnote). These observations need more investigation – the possible false positive could be investigated using a viral neutralisation assay to determine whether the plasma is in fact a true positive.
- At present, taken together, these data suggest that the EuroImmun assay has specificity in the region of 97 99%. Running larger number of known negative samples through this assay is required to obtain a more accurate estimate of specificity.
- Newer anti-N EIAs from Roche and Abbott are also available, and may be deployed in the NHS.

Sensitivity: The sensitivity of a test refers to the proportion of individuals with the condition who test positive. According to our current understanding:

- Sensitivity of detection rises over time. Median IgG seroconversion was 13 days post duration of symptoms in a large Chinese study (5), compatible with smaller studies (4). By 21-days post symptoms, almost all seroconversion had occurred (5).
- Individuals with severe illness vs. milder clinical illness had higher titres early on (before 14 days) but cases with mild disease achieved similar titres to severe disease later (5).
- The sensitivity of detection of historical COVID-19 disease is probably about 80% (5).

¹ PHE "Evaluation data for Euroimmun IgG ELISA for SARS-CoV-2 antibodies" validation report 28-3-2020, [name]

Evaluating Detection of SARS-CoV-2 antibodies using home test kits (EDSAB-HOME study)

Protocol 30.05.2020 Version 04.03

- Viral mutation is one possible explanation for low sensitivity, especially if very short domains or a small number of peptides are used as antigens (6).
- The sensitivity of diagnosis of SARS-CoV-2 by serological means has not been established in the UK.
- Studies indicate that in people exposed to a household case of COVID-19, a proportion (perhaps 25%) develop antibodies, as detected by anti-S protein EIAs. Whether the other household members were uninfected, or were infected but did not detectable antibody, is unknown (5).

Table 1: Assessment of specificity: sera from historical samples considered low risk for SARS-CoV-2 infection

		Eurolmmun assay result			
Test set	Negative	Indeterminate	Positive	Specificity	
Porton	90	1	1	99%	
Negative					
control set					
(n=92)					

Data extracted from PHE "Evaluation data for Euroimmun IgG ELISA for SARS-CoV-2 antibodies" validation report 28-3-2020, [name]

Table 2: Assessment of sensitivity: sera from known positive cases

	Eurolmmun assay result			
Days post onset	Negative	Indeterminate	Positive	Sensitivity
0-4	18	0	0	0
5-14	18	3	12	46%
15-28	6	1	19	73%
>28	No data			

Data extracted from PHE "Evaluation data for Euroimmun IgG ELISA for SARS-CoV-2 antibodies" validation report 28-3-2020, [name]

Clinical utility

